## 7.5.3.2 Exploratory Endpoints

Summary statistics will be tabulated for microsatellite instability, CMS1, CIMP, KRAS and BRAF status. Paired t-test or Wilcoxon signed rank test will be used to assess the changes in biomarkers pre- and post-treatment. The differences in biomarker levels between responders and non-responders will be assessed using  $X^2$  or Fisher's exact test as appropriate. Similar analysis will be used to assess the correlation between biomarker mutation statuses.

Statistical analyses will be conducted by MDACC statisticians. Tabulations will be produced for appropriate demographic, baseline, efficacy and safety parameters. For categorical variables, summary tabulations of the number and percentage of subjects within each category (with a category for missing data) of the parameter will be presented, as well as two-sided 95% confidence intervals, unless otherwise stated. For continuous variables, the number of subjects, mean, median, standard deviation (SD), minimum, and maximum values will be presented. Time-to-event data will be summarized using Kaplan-Meier methodology using 25th, 50th (median), and 75th percentiles with associated 2-sided 95% confidence intervals, as well as percentage of censored observations.

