## 6.4.5 Biomarkers

Due to limited understanding of the biological activities induced by M7824 in cancer subjects, there can be no certainty that the doses examined will be associated with relevant antitumor immune activities. Further details regarding translational studies are listed in Appendix 3. As the consequence, the trial will serve to

- 1. Evaluate MSI-H status with CMS subtype
  - a. MSI will be assessed by MSI-H CRC either by IHC for loss of protein expression in one of 4 mismatch repair proteins (MLH1, MSH2, MSH6, PMS2) or by detection of microsatellites within the tumor DNA (as per institutional practices)
  - b. External MSI testing in a CLIA certified laboratory with a documentation of MSI-H status performed prior to screening is acceptable for inclusion in cohort A- C.
- 2. Evaluate PD-L1 expression as a predictor of response
  - a. Primary tumor will be stained for PD-L1 expression by IHC
  - b. PD-L1 staining will be semi-quantitatively scored by absence, weak, moderate, strong by a pathologist

- c. The above will be performed on the mandatory fresh on-treatment biopsy.
- 3. Evaluate the effect on TGF $\beta$  concentrations in plasma.
- 4. Evaluate potential predictive / prognostic biomarker candidates related to the drug and / or the cancer (such as the CMS, immune infiltrating populations, systemic cytokine profiles)
  - a. CMS will be assessed using a 75 gene FFPE based assay using the Nanostring technology in a CLIA-certified laboratory at MD Anderson.
    - i. Current discovery of 74 samples run in 18 batches with random duplicate samples to assess technical validity demonstrate accuracies compared to gold standard gene expression by Affymetrix hybridization:
      - 1. A 75 gene model had 4 group CMS accuracy of 87.1% with very high accuracies (>90%) in CMS1 and CMS2 groups which were over-represented in this small cohort
      - 2. The CMS4 versus other subgroups demonstrated accuracy of 90.6%
      - 3. The Nanostring technology on FFPE has been successfully applied to breast cancer and lymphoma cohorts
      - 4. The Nanostring codesets utilized for the CMS classification are now being assessed for technical validity in MDA's CLIA molecular pathology laboratory
  - b. Immune infiltrating populations will be analyzed by immunohistochemistry (IHC), and Multiplex IF analyses.

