## 7.3.3 Exploratory Endpoints

The exploratory endpoints for this study are:

- Changes in intratumoral immune populations, gene expression and proteomic profiles pre and post-treatment with M7824 where paired biopsies are available
- Changes in circulating immune cell populations and cytokine profiles pre and post-treatment with M7824
- Circulating levels of TGF-β collected from serial plasma samples.

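### The only tests named for comparing biomarker levels between responders and non-responders are chi-square and Fisher's exact, which continuous markers cannot use without a cut-point, and the plan gives none

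*Combined protocol and SAP*

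**What the plan says.** Section 7.5.3.2 (Exploratory Endpoints) gives three rules in a row.

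- Change over time: "Paired t-test or Wilcoxon signed rank test will be used to assess the changes in biomarkers pre- and post-treatment".
- Responders against non-responders: "The differences in biomarker levels between responders and non-responders will be assessed using" chi-square "or Fisher's exact test as appropriate".
- Mutation markers: "Similar analysis will be used to assess the correlation between biomarker mutation statuses".

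The markers are of three kinds.

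- **Continuous.** Section 7.3.3 lists "Changes in circulating immune cell populations and cytokine profiles pre and post-treatment with M7824" and "Circulating levels of TGF-β collected from serial plasma samples". Sections 6.4.5 and 6.4.5.2 add intratumoral immune populations and soluble factors.
- **Ordinal.** In Section 6.4.5, "PD-L1 staining will be semi-quantitatively scored by absence, weak, moderate, strong by a pathologist".
- **Categorical.** MSI, CMS, CIMP, KRAS and BRAF status.

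Two places ask for a link to outcome. Exploratory objective 7 in Section 3.3 relates response to PD-L1. Section 6.4.5.3 plans to look for an association between a panel of markers, circulating TGF-β among them, and clinical efficacy. Nothing in Sections 6.4.5 or 7.5 names a rank-sum test, a two-sample t-test, a trend test or a cut-point for the responder comparison.

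**The concern.** Chi-square and Fisher's exact test analyse counts in a table, and the phrase about appropriateness chooses only between those two. A concentration or cell count enters such a table only after grouping. An analyst who follows the plan must therefore choose a cut-point, possibly with the data in view, and one who does not must depart from the plan.

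The neighbouring sentences make it hard to read the rule as meant for categorical markers only. The sentence before it gives biomarkers a paired t-test or signed-rank test, which presupposes an ordered or continuous scale. The sentence after it deals with mutation status separately.

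At stake is how reliable the response-biomarker findings are in cohorts of 15 to 29 patients, where there is little information to spare.

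**Working it through.** **1. Inputs.** The plan attaches no sample size, alpha or power to this comparison, so there is no stated figure to reproduce. Cohort sizes come from Section 7.1: 15 (A-C), 29 (B) and 15 (D). Cohort B needs at least 4 responders and targets 25%, and 0.25 × 29 = 7.25, so about 7. As a check on N, let X1 be the responders among the first 15 patients and X2 those among the next 14. Early termination is P(X1 ≤ 1), and success is the sum over x ≥ 2 of P(X1 = x) · P(X2 ≥ 4 − x). At 5% these give 0.829 and 0.0418, and at 25% success is 0.9001. The plan states 82.9%, 0.042 and 90%, so they agree.

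**2. Chi-square on ungrouped continuous values.** With all values distinct, the table has N rows of one patient each. Let r be the responders and s the non-responders. A responder's row contributes (s/N)²/(r/N) + s/N = s/r, and a non-responder's row contributes r/s. The total is r(s/r) + s(r/s) = N, whatever the data. For N = 29 this is 29 on 28 df (p = 0.41), and for N = 15 it is 15 on 14 df (p = 0.38). The test says nothing until the values are grouped.

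**3. Smallest attainable p with 15 patients.** A median split gives groups of 7 and 8. If all m responders fall in the group of 7, Fisher's p is C(7,m)/C(15,m). The opposite extreme is more probable (28/105 or 56/455), so it adds nothing.

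- m = 2: 21/105 = 0.20. The exact rank-sum minimum is 2/105 = 0.019.
- m = 3: 35/455 = 0.077. The exact rank-sum minimum is 2/455 = 0.004.

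The Fisher minimum is the same whichever group takes the median patient.

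**4. Simulated power.** Assumptions: normal marker, equal SD, higher values in responders, two-sided 5% level, pooled median split with the median patient in the lower group. Repeats with 6,000 to 40,000 runs per scenario differ by no more than about 0.02.

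| Responders v non-responders | Shift | Rank-sum | Fisher |
|---|---|---|---|
| 7 v 22 | 1 SD | 0.57 | 0.49 |
| 7 v 22 | 1.5 SD | 0.89 | 0.78 |
| 5 v 10 | 1 SD | 0.33 | 0.14 |
| 5 v 10 | 1.5 SD | 0.63 | 0.36 |
| 4 v 11 | 1 SD | 0.29 | 0.27 |
| 4 v 11 | 1.5 SD | 0.58 | 0.52 |
| 4 v 25 | 1 SD | 0.38 | 0.39 |
| 4 v 25 | 1.5 SD | 0.69 | 0.66 |

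**5. The median patient.** Both cohort sizes are odd, so one patient must be assigned to a side.

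- 4 v 25, all four responders high: with an upper group of 14, p = C(14,4)/C(29,4) = 1001/23751 = 0.042. With an upper group of 15, p = (1365 + 1001)/23751 = 0.100. Power at 1 SD goes from 0.39 to essentially 0.
- 7 v 22, six of seven high: p moves from 0.035 to 0.080, and power at 1 SD from 0.49 to 0.17.
- 5 v 10: the change goes the other way, from about 0.14 to about 0.25.

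**6. Ordinal marker.** Take four levels with assumed probabilities 0.05/0.15/0.30/0.50 in responders and 0.40/0.30/0.20/0.10 in non-responders. A permutation chi-square on the 2×4 table has power 0.63 against 0.78 for a permutation rank-sum (7 v 22), and 0.30 against 0.43 (4 v 11). The unordered test is valid here; at 7 v 22 with equal probabilities it rejected 4.2% of the time.

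**The case against.** The sentence sits among categorical markers, for which the named tests are right, so the likeliest error is an omitted rule for continuous markers. Section 6.4.5 calls all the biomarker analyses exploratory. Section 7.5.1 says that data will be presented descriptively, and Section 7.5.3.2 already asks for means, medians and SDs of continuous variables. All of this stands and limits the consequence. It does not supply a two-group test or a cut-point.

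A reader might infer more than the documents support in four ways.

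- **That PD-L1 must be dichotomised, or that the named tests are invalid for it.** The score already has four categories, so a 2×4 test runs with no cut-point. It loses efficiency, not validity.
- **That the TGF-β analysis in Section 7.3.3 is itself mis-specified.** That entry and objective 3 concern levels and their change, and pre/post changes have suitable paired tests. The link to efficacy comes from Section 6.4.5.3, among assessments to be considered.
- **That Fisher's test always loses power.** At 4 v 25 and 1 SD it does not, and the size of the loss elsewhere shifts with the handling of the median patient.
- **That the rank-sum test is the only acceptable replacement.** Under the normal model the t-test does slightly better (0.62 at 7 v 22, 1 SD).

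**Conclusion.** The point holds for continuous markers: the only rule given cannot be applied as written, and the grouping it needs is undefined. For ordinal PD-L1 the rule is workable but inefficient. For categorical markers it is correct.

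The exact results (the chi-square that always equals N, and the minimum p of 0.20 or 0.077 with 2 or 3 responders of 15) need no distributional assumption; the second does assume a median split. The power figures rest on assumed effect sizes, responder counts, a normal marker, the 5% level and one split convention. They show a usual direction, not a stable amount. They do not measure the harm from a cut-point chosen after seeing the data, which remains a qualitative concern.

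Label: wrong as written. Severity: minor. The primary endpoints, sample size and stopping rules are unaffected.

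**What to change.** Replace the one sentence in Section 7.5.3.2 with a rule by scale of measurement:

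- **Continuous levels** (TGF-β, cytokines, immune-cell populations): exact Wilcoxon rank-sum test, or a two-sample t-test where suitable, with a location difference and confidence interval.
- **Ordinal scores** (PD-L1): rank-sum or exact trend test, with counts by category. A Hodges-Lehmann difference is not meaningful for this score and should not be attached to it.
- **Categorical markers** (KRAS, BRAF, CIMP, CMS, MSI): chi-square or Fisher's exact test, as now.
- **Any cut-point**: stated before the data are examined, including which side takes values equal to it.

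The cost is a short text amendment. It needs no new data, assays or patients.

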## 7.5.3.3 Adverse Events

Severity of AEs will be graded using the NCI-CTCAE v4.03 toxicity grading scale. Safety will be assessed by descriptive statistics and summarized in tabular format. This data will be separated based on organ class, immune-relation, severity and relation to M7824.

Adverse events (serious and non-serious) will be considered treatment emergent adverse events when emerging in the on-treatment period defined as the time from the first trial drug administration to the last drug administration date + 30 days or the earliest date of subsequent anticancer drug therapy minus 1 day, whichever occurs first, unless otherwise stated. All premature terminations will be summarized by primary reason for treatment withdrawal.

## 7.5.3.4 Laboratory Variables

Laboratory results will be classified by grade according to NCI-CTCAE v4.03. The worston-trial grades after the first trial treatment will be summarized. Shifts in toxicity grading from first treatment to highest grade will be displayed. Results for variables that are not part of NCI-CTCAE will be presented as within or above normal limits. Only subjects with post-Baseline laboratory values will be included in these analyses.

# 7.5.3.5 Physical Examination, Including Vital Signs and 12-Lead Electrocardiogram

Vital signs (body temperature, respiratory rate, heart rate, and blood pressure), eye signs and symptoms based on System Organ Class of "eye disorders", and 12-lead EKG recorded according to the Schedules of Assessments (refer to **Tables 1-3**) will be presented.

## 7.6 Interim safety monitoring

For each cohort, we will implement Bayesian toxicity monitoring such that we will all stop patient enrollment into a cohort if there is a high probability that the AE rate of M7824 is greater than 20%. For each cohort separately, we will apply the toxicity monitoring rule in cohort size of 5, starting from the 5th patient. For cohort A-C, the toxicity stopping rule to be applied is as follows: Stop patient enrollment in a cohort if Prob(p>0.20 |data ) > .75, where p denotes the probability of toxicity.

Assuming a beta(.4, 1.6) priori for p, the above decision criterion implies that we will stop cohort A or cohort C according to **table 8** below.

Table 8: Toxicity stopping boundaries for Cohort A-C and D

Number	of	evaluable	Number	of	patients	with
patients			toxicities	is at l	least	
5			2			
10			4			
15			5			

The operating characteristics for toxicity monitoring in cohort A-C are illustrated in Table 9.

 Table 9: Operating Characteristics for Toxicity Monitoring in Cohort A-C and D

True toxicity rate	Prob (stop early)	Average Sample Size
0.10	0.086	14.2
0.20	0.284	12.3
0.30	0.532	10.0
0.40	0.750	8.0
0.50	0.894	6.5

Similarly for cohort B, the toxicity stopping rule to be applied is as follows: Stop patient enrollment if Prob(p>0.20 | data ) > .85, where p denotes the probability of toxicity. Assuming a beta(.4, 1,6) priori for p, the above decision criterion implies that we will stop cohort B according to **table 10** below.

Number	of	evaluable	Number of patients with
patients			toxicities is at least
5			3
10			4
15			5
20			7
25			8
29			9

#### Table 10: Toxicity stopping boundaries for Cohort B

The operating characteristics for toxicity monitoring in cohort B are illustrated in Table 11.

True toxicity rate	Prob (stop early)	Average Sample Size
0.10	0.25	28.5
0.20	0.238	24.9
0.30	0.623	18.4
0.40	0.900	12.3
0.50	0.989	8.7

Table 11: Operating Characteristics for Toxicity Monitoring in Cohort B

The stopping boundaries and the operating characteristics for cohorts A-C and B were generated using Shiny application for Bayesian toxicity monitoring (http://qctrlshiny/postprobtoxicity).

AEs of 3 or greater and deemed related to M7824 (section 6.4.1.1.1) will count towards toxicity calculations with respect to interim safety monitoring. AEs of 3 or greater deemed unrelated to M7824 are not included towards safety decision making. These include AEs attributable to disease progression (section 6.4.1.1.2) and abnormal laboratory or investigational values that are asymptomatic or do not result in treatment discontinuation (section 6.4.1.1.1).

The time period that grade 3 AEs attributable to M7824 are counted towards interim safety monitoring decisions is defined from their onset to 90 days after the last dose of study drug (section 6.4.1.1.3).

Any grade 5 event on-study will require suspension of the study pending review of the safety data regarding the death.

The Investigator is responsible for completing an efficacy/safety summary report, and submitting it to the IND Office Medical Affairs and Safety Group, for review and approval. This should be submitted after the first 5 evaluable patients per cohort, complete 1 cycle of study treatment, and every 5 evaluable patients per cohort, thereafter. On every report submission, the information from previous reported patients will need to be updated.

A copy of the cohort summary should be placed in the Investigator's Regulatory Binder under "IND Office correspondence".

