# 7.1.2 The total sample size of this cohort is 15 patients. With this sample size, the half-width of the 95% confidence interval for the estimated response rate will be at most 0.253. Cohort B

For this cohort, the Simon's Optimum two-stage design will be implemented. A historical response rate of 5% and a target response rate of 25% are assumed under the null and the alternative hypotheses, respectively. In the first stage, we will enroll 15 patients; if 1 or fewer achieves a best response of CR/PR, we will stop enrolling patients. Otherwise, we will continue to enroll all 29 patients and the treatment is deemed as promising if there are 4 or more responders out of these 29 patients. The design has a type I error rate of 0.042, a 90% power and a probability of early termination of 82.9% under the null hypothesis. Patient enrollment will be temporarily suspended when the enrollment for the first stage patients has been completed yet not enough responders have been observed to trigger the start of second stage.

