## 7.5.2 Analysis of Primary Endpoint

### 7.5.2.1 Response Rate

## 7.5.2.1.1 Cohorts A-C and B

Patient response will be determined using iRECIST 1.1. Unconfirmed responses will not be used in the final analysis. ORR is defined by the number of (PR + CR)/(total number of treatedpatients) in the safety analysis set. For all cohorts, we will estimate the response rate along withthe two-sided exact 95% confidence interval. Also for Cohort B, if the trial continues to the fullenrollment of 29 patients, we will declare M7824 with radiation promising and worthy of furtherinvestigation if there are at least 4 responders out of these 29 patients.

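### Two stated operating figures are wrong: Table 11 prints a 25% early-stop probability where the rule gives 2.5%, and the 15-patient half-width bound of 0.253 is exceeded by the planned exact interval (0.261)

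*Combined protocol and SAP*

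**What the plan says.** **Toxicity monitoring, Cohort B (Section 7.6).** The rule is "Stop patient enrollment if Prob(p>0.20 | data ) > .85", with a prior introduced as "Assuming a beta(.4, 1,6) priori for p". The comma in the second parameter is a slip for 1.6, the value given for Cohort A-C. On timing, "we will apply the toxicity monitoring rule in cohort size of 5, starting from the 5th patient". Table 10 turns this into stopping at 3 or more toxicities among 5 patients, 4 among 10, 5 among 15, 7 among 20, 8 among 25 and 9 among 29. The text then says: "The operating characteristics for toxicity monitoring in cohort B are illustrated in Table 11". The Table 11 row for a true rate of 0.10 is "0.10 0.25 28.5" (true rate, probability of stopping early, average sample size). The next row, for a true rate of 0.20, shows 0.238 and 24.9.

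**Precision, Cohorts A-C and D (Sections 7.1.1 and 7.1.3).** Each has 15 patients, and for each "the half-width of the 95% confidence interval for the estimated response rate will be at most 0.253". The Cohort A-C sentence is printed under the 7.1.2 heading. Section 7.5.2.1.1 says that the response rate in all cohorts will be reported with a "two-sided exact 95% confidence interval".

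**The concern.** Table 11 is where a reader learns how often the safety rule would halt a combination whose true toxicity is half the 20% limit. As printed, that happens in one trial in four; under the stated boundaries it happens in about one in forty. A reader who trusts the table could judge the rule far too sensitive and ask for it to be loosened.

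The half-width sentence is the only sample-size justification for two of the three cohorts. It is worded as an upper bound, and the bound does not hold for the interval that the plan intends to report.

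**Working it through.** **1. Table 11, true toxicity 0.10**

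*Boundaries.* With a Beta(0.4, 1.6) prior and x toxicities among n patients, the posterior is Beta(0.4 + x, 1.6 + n − x). The smallest x with posterior probability of p > 0.20 above 0.85 is 3, 4, 5, 7, 8 and 9 at n = 5, 10, 15, 20, 25 and 29. Table 10 reproduces in full.

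*Other rows of Table 11.* Carry the binomial distribution of the toxicity count from look to look and remove the paths that reach a boundary. A stop at 5, 10, 15, 20 or 25 counts as early, since 29 is full enrolment.

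| True rate | P(stop early), printed | computed | Average N, printed | computed |
|---|---|---|---|---|
| 0.10 | **0.25** | **0.025** | 28.5 | 28.5 |
| 0.20 | 0.238 | 0.237 | 24.9 | 25.0 |
| 0.30 | 0.623 | 0.626 | 18.4 | 18.3 |
| 0.40 | 0.900 | 0.901 | 12.3 | 12.4 |
| 0.50 | 0.989 | 0.987 | 8.7 | 8.8 |

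The Cohort A-C and D figures in Table 9 reproduce the same way: probabilities within 0.005, average sizes within 0.1. Only one cell fails.

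*That cell, look by look at p = 0.10.*

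- n = 5: P(X ≥ 3) = 10(0.1)³(0.9)² + 5(0.1)⁴(0.9) + (0.1)⁵ = 0.00810 + 0.00045 + 0.00001 = 0.00856. The surviving counts 0, 1 and 2 have probabilities 0.59049, 0.32805 and 0.07290.
- n = 10 (stop at 4): 0.59049 × P(X ≥ 4) + 0.32805 × P(X ≥ 3) + 0.07290 × P(X ≥ 2), with X from 5 new patients, = 0.59049 × 0.00046 + 0.32805 × 0.00856 + 0.07290 × 0.08146 = 0.00902.
- n = 15, 20 and 25, by the same step: 0.00613, 0.00036 and 0.00053.
- Total: 0.0246. A simulation of 400,000 trials also gives 0.0246. If the look at 29 also counts as a stop, the total is 0.0249.
- Average N = 5(0.00856) + 10(0.00902) + 15(0.00613) + 20(0.00036) + 25(0.00053) + 29(0.9754) = 28.5, which matches the printed value.

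*Two checks that need no software.*

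- With boundaries that stop at a given number of toxicities or more, raising the true rate cannot lower the chance of stopping. The table has it falling from 0.25 at 10% toxicity to 0.238 at 20%.
- The last early look is at 25 patients. If 25% of trials stopped early, the average could be at most 0.25 × 25 + 0.75 × 29 = 28.0. The same row prints 28.5.

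**2. Half-width with 15 patients**

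*The plan's figure.* The normal-approximation (Wald) half-width at p = 0.5 is 1.96 × √(0.25/15) = 0.253. This reproduces the stated value.

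*The planned method.* The exact (Clopper-Pearson) limits for r responders of 15 are the 2.5% quantile of Beta(r, 16 − r) and the 97.5% quantile of Beta(r + 1, 15 − r).

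| Responders | Exact 95% interval | Half-width |
|---|---|---|
| 5 | 0.118 to 0.616 | 0.249 |
| 6 | 0.163 to 0.677 | 0.257 |
| 7 | 0.213 to 0.734 | 0.261 |
| 8 | 0.266 to 0.787 | 0.261 |
| 9 | 0.323 to 0.837 | 0.257 |

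The exact half-width therefore exceeds 0.253 at 6, 7, 8 and 9 responders, and its maximum is 0.261.

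**The case against.** On Table 11, the arithmetic is not in dispute, but the error can be called trivial. It looks like a dropped zero in one cell. Enrolment stops on the Table 10 boundaries, which are correct, so conduct is unaffected. The slip makes the design look worse rather than better, and the correct 28.5 beside it would alert a careful reader. All of that stands, and it limits the seriousness of the point. It does not make the figure right: the table exists to describe how the safety rule behaves. A fault in reading the PDF cannot be fully excluded, but nothing points to one, and every other stop probability in Tables 9 and 11 is printed to three decimals. The comparison takes a stop at full enrolment as not early, which the plan does not define. The choice matters for matching the other rows, but not for this cell, which is 0.025 either way.

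On the half-width, the objection is stronger. The 0.253 is correctly calculated as a customary planning approximation, and Sections 7.1.1 and 7.1.3 do not call it exact. The gap is at most 0.008, occurs at four of the sixteen possible outcomes, and changes no sample size or decision. For Cohort D, the exact method rests on the reference to all cohorts in Section 7.5.2.1.1, which is headed for Cohorts A-C and B; Cohort D's own analysis section names no interval method. These points make this part minor. What remains is that an unqualified upper bound is false for the interval that will be reported.

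**Conclusion.** The concern holds on both counts. The Table 11 early-stop probability at 10% toxicity is 0.025, not 0.25, an overstatement by a factor of 10 confined to that cell. This rests on the Table 10 boundaries and looks after every 5 patients, and it is supported by the inconsistency within the table itself. The stated maximum half-width of 0.253 should be 0.261 for the exact interval, a difference of 0.008. For Cohort D this assumes that the exact method in Section 7.5.2.1.1 applies there too. Boundaries, sample sizes and decision rules are unaffected. The two figures should be corrected, mainly because of the first.

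**What to change.** - Table 11, row for true toxicity 0.10: change the early-stop probability from 0.25 to 0.025. Leave the average sample size at 28.5.
- Sections 7.1.1 and 7.1.3: give the maximum half-width as 0.261 and say that it refers to the exact 95% interval. Labelling 0.253 as a normal approximation would also remove the error, but 0.261 matches the planned analysis.

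The cost is three corrected figures. The stated precision for the 15-patient cohorts becomes slightly less favourable.

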#### 4.1.3 Planned treatment duration

The trial duration for a subject is estimated to be up to 2 years. This includes an 28-day screening period (decision will be made in this period for subject's trial inclusion if all eligibility criteria are met), a treatment duration until confirmed PD, unacceptable toxicity, or any criterion for withdrawal from the trial or IMP occurs (see Section 4.5) and an 28-Day Safety Follow-up visit 4 weeks after the last dose of M7824 administration.

Subjects who have experienced a durable, confirmed PR or CR may continue treatment for a maximum of 12 months, although additional treatment is possible. If the Investigator believes that a subject may benefit from treatment beyond 12 months, it may be permissible after discussion with the principal investigator. In the case of pseudoprogression, subjects should continue treatment through one additional tumor assessment, if they meet the criteria described in Section 4.5.1.

Adverse events (AEs) and adverse drug reactions (ADRs) should be followed until they resolve, return to baseline, or are irreversible (see Section 6.1.4 for details).

In both cohorts, it is anticipated to enroll the first planned subject by October 2017, and the final subject enrolled by October 2018.

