### 5.5.3 Special Precautions

As a routine precaution, subjects all enrolled in this trial must be observed for 2 hours in the CTRC post end of infusion, in an area with resuscitation equipment and emergency agents at least for the first two doses of treatment with M7824. If no medical problems arise during the first two treatments, then the 2 hour observation period does not need to continue starting with the third dose of treatment. At all times during M7824 treatment, immediate emergency treatment of an infusion-related reaction or a severe hypersensitivity reaction according to institutional standards must be assured. In order to treat possible anaphylactic reactions, for instance, dexamethasone 10 mg and epinephrine in a 1:1000 dilution or equivalents should always be available along with equipment for assisted ventilation.

Infusion of M7824 will be stopped in case of Grade  $\geq 2$  hypersensitivity, inflammatory response, or anaphylactic reaction. The treatment recommendations for infusion-related reactions and severe hypersensitivity reactions according to the NCI are outlined in Sections 5.5.3.1 and 5.5.3.2, respectively.

Investigators should also monitor subjects closely for potential irAEs (described in Section 5.5.3.3), which may become manifest after several weeks of treatment. Such events may consist of persistent rash, diarrhea and colitis, autoimmune hepatitis, arthritis, glomerulonephritis, cardiomyopathy, or uveitis and other inflammatory eye conditions.

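### Tables 9 and 11 assume complete toxicity data at every look and no accrual while waiting; under the look timing in Section 7.6 a cohort with true toxicity above 20% is stopped later, and less often to the extent that events arise after cycle 1

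*Combined protocol and SAP*

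**What the plan says.** Section 7.6 stops enrolment into a cohort "if there is a high probability that the AE rate of M7824 is greater than 20"%. The rule is applied in blocks of 5, starting at the fifth patient. For Cohort A-C it reads "Stop patient enrollment in a cohort if Prob(p>0.20 |data ) > .75", and Table 8 extends the same bounds to Cohort D. Cohort B uses a threshold of 0.85.

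The text after Table 11 sets the timing. On the summary report: "This should be submitted after the first 5 evaluable patients per cohort, complete 1 cycle of study treatment", and then after every further 5 evaluable patients, with earlier patients' data updated each time. Section 6.1.2 defines a cycle as 28 days. The counting period for grade 3 events attributed to the drug "is defined from their onset to 90 days after the last dose of study drug". Under Section 4.1.1, treatment continues until progression or unacceptable toxicity. Section 5.5.3 says of immune-related events that they are ones "which may become manifest after several weeks of treatment".

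Section 7.6 presents Table 9 as describing this rule: "The operating characteristics for toxicity monitoring in cohort A-C are illustrated in Table 9". Table 11 does the same for Cohort B. Both come from a web application, and no input for accrual or late events is described.

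**The concern.** The look and the definition of toxicity run on different clocks. A patient may have only 28 days of follow-up when the boundary is checked, while the rule counts events over the whole of dosing plus 90 days. An event after the look is added at the next block. In a 15-patient cohort the 10-patient look is the last that can prevent enrolment, so later updates come too late to matter there.

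Tables 9 and 11 are the plan's evidence that the rule protects patients. If they describe a trial with instant, complete information, a cohort with unacceptable toxicity would expose more patients than a reader of those tables would expect.

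**Working it through.** **Inputs (Section 7.6).** Limit 20%. Prior: "Assuming a beta(.4, 1.6) priori for p". Bounds for A-C and D: 2/5, 4/10, 5/15. Bounds for B: 3/5, 4/10, 5/15, 7/20, 8/25, 9/29. Accrual (Section 4.1.3): "it is anticipated to enroll the first planned subject by October 2017, and the final subject enrolled by October 2018", that is, about 12 months.

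**Step 1: bounds.** Each bound is the smallest x with 1 − BetaCDF(0.20; 0.4 + x, 1.6 + n − x) above the threshold. For 2 of 5 this is 0.778 (> 0.75); for 3 of 10 it is 0.720 (no stop); for 4 of 10 it is 0.895. All bounds in Tables 8 and 10 reproduce.

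**Step 2: the stated figures, with complete information.** A-C and D at p = 0.40:
- Stop at 5: 1 − 0.6⁵ − 5(0.4)(0.6⁴) = 1 − 0.0778 − 0.2592 = 0.6630.
- Stop at 10: 0.0778 × P(≥4 of 5) + 0.2592 × P(≥3 of 5) = 0.0778 × 0.0870 + 0.2592 × 0.3174 = 0.0890.
- P(stop early) = 0.752 (stated 0.750).
- Average n = 5(0.6630) + 10(0.0890) + 15(0.2479) = 7.92 (stated 8.0).

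The same recursion at 10, 20, 30, 40 and 50% gives 0.085, 0.289, 0.536, 0.752, 0.897 for Table 9 (stated 0.086, 0.284, 0.532, 0.750, 0.894). For Table 11 it gives 0.025, 0.237, 0.626, 0.901, 0.987 (stated 0.25, 0.238, 0.623, 0.900, 0.989). Average sample sizes agree within 0.1. The 0.25 looks like a slip for 0.025, since its stated average n of 28.5 fits 0.025; that is a separate matter. A stop at the last patient is not counted as early. So the tables are the complete-information, no-accrual figures.

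**Step 3: the rule as written.** Simulation with random arrivals that fill each cohort in 12 months on average. Look n falls 28 days after patient n enters, earlier patients are updated at every look, and there is no hold. Onset is uniform over an assumed window. At 40% true toxicity (P(stop early) / average n):

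| Onset window | Share in cycle 1 | A-C and D | B |
|---|---|---|---|
| Stated | – | 0.750 / 8.0 | 0.900 / 12.3 |
| 28 days | 100% | 0.75 / 8.7 | 0.89 / 14.4 |
| 8 weeks | 50% | 0.68 / 9.7 | 0.86 / 16.2 |
| 12 weeks | 33% | 0.59 / 10.5 | 0.81 / 18.0 |
| 24 weeks | 17% | 0.38 / 12.4 | 0.59 / 23.0 |

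A different onset model, with 75% down to 25% of events in cycle 1 and the rest uniform over weeks 4 to 26, gives 0.65 / 9.9 to 0.40 / 12.2 for A-C and D, and 0.82 / 17.1 to 0.60 / 22.7 for B.

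**Step 4: separating the two causes.** With all onset in cycle 1, only the missing hold is at work. At 30–50% toxicity, stopping probability moves by about 0.01, while average n rises by about 0.6 to 1.1 (A-C and D) or 1.3 to 2.2 (B). With half the events after cycle 1 and 40% toxicity, a 4-week hold at each look gives 0.55 / 10.3 against 0.54 / 11.0 without one (A-C and D), and 0.79 / 17.3 against 0.72 / 19.9 (B). Late onset drives the loss in stopping probability; a hold recovers little of it in A-C and D and part of it in B.

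**The case against.** **The tables contain no arithmetic error.** This stands. They are the standard operating characteristics given the toxicity status known at each look. The point is an unstated assumption that the plan's own timing does not meet.

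**The size rests on onset times that the documents do not give.** This also stands. Section 5.5.3 says only that immune-related events can appear late, and the rule counts all related grade 3 or greater events. Section 2.2.6.1 reports that most infusion reactions to the parent antibody began at the first or second infusion, which here fall in cycle 1. A reader might take the 24-week figures as the expected loss; the documents do not support that. The 28-day row belongs in the range, and there stopping probability is essentially intact.

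**Late events can be acted on by other routes.** Partly true. A grade 5 event suspends the study, Section 4.6 allows discontinuation for an unexpectedly high incidence of known reactions, and Section 6.4.1.4 requires prompt reporting of serious events. None of these applies the numerical boundary to which Tables 9 and 11 refer. The updating of earlier patients is already in the simulation. Counting everyone enrolled at the look, a more generous reading, still gives 0.63 or 0.40 (A-C and D) and 0.83 or 0.61 (B) for 12 or 24 weeks.

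**Parts of the timing are inferred.** The one-cycle condition is explicit only for the first 5 patients; applying it to later blocks is natural but unstated. Evaluable is not defined, and Section 7.6 is silent on enrolment during review. Cohort B has a conditional pause after stage 1, but it depends on responses and is not modelled here. The accrual sentence in Section 4.1.3 refers to two cohorts; using 12 months for each of three is an assumption.

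**Conclusion.** The point holds as a mismatch between the monitoring rule and its stated operating characteristics. At true toxicity above 20%, average sample size is understated even if all events occur in cycle 1, and stopping probability is overstated to the extent that they occur later. At 40% toxicity the range is 0.75 / 8.7 to 0.38 / 12.4 for Cohorts A-C and D, and 0.89 / 14.4 to 0.59 / 23.0 for Cohort B. These figures assume 12-month accrual per cohort, looks at 28 days for every block, no hold and uniform onset.

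Two stronger readings are tempting and fail. One is that the tables are too favourable throughout: at 10–20% toxicity they overstate stopping, which there means false stops, so on that side they are pessimistic. The other is that the missing enrolment hold is what undermines stopping: it mainly adds patients, and a 4-week hold would not restore the stated figures if a material share of events is late.

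**What to change.** In Section 7.6:

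1. Re-simulate and restate Tables 9 and 11 under the actual look timing and accrual, and under a stated onset range that includes early onset. Define evaluable, say whether one cycle applies to every block, and say whether enrolment continues during a look.
2. Keep the 5-patient reports and add a boundary check whenever a qualifying event is reported. Count all treated patients and use the bound for the next tabulated sample size. For Cohorts A-C and D: at least 2 with up to 5 treated, 4 with 6–10, 5 with 11–15. Do not recompute the posterior at every n: with onset within 28 days, that gives false-stop risks of 0.106 to 0.138 at 10% toxicity.
3. Report the false-stop risk of the added check across the onset range.

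**Gain.** At 40% toxicity, event-triggered checking brings A-C and D to about 0.69–0.71 / 9.2 (12-week onset) or 0.53 / 11.4 (24-week onset).

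**Cost.** Wording and one simulation; no dose or individual treatment rule changes. For A-C and D, false stops at 10% toxicity are about 0.03 to 0.09, close to or below the stated 0.086. At 20% they reach up to about 0.31 against the stated 0.284, which is the small downside. The published stopping figures at toxic rates will look less favourable over most of the onset range.
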